The primary observation to be made is the level of PaCO₂ in the arterial blood, specifically when the patient is insufflated and deflated during the surgery. As a result of the consistent pressure that the AirSeal® system maintains, CO₂ will be absorbed in lower levels when compared to the standard of care systems in which fluctuations in intra-peritoneum pressure are seen. Therefore, higher pressures will result in higher levels of CO₂ exchange in the blood, leading to increased vasodilation and lower pH levels.⁸ Given the potential benefit of using valve-less trocars during robotic prostatectomies as demonstrated in other laparoscopic abdominal procedures, the aims of this study are:

Aim #1) Describe the perioperative CO₂ absorption rates between the conventional and valve-less trocar groups via the end-tidal CO₂ and PaCO₂, at baseline, 60 minutes intraoperatively, and immediately following surgery. Optimal intraoperative levels for PaCO₂ and end tidal CO₂ should be between 33-37 mmHg. These values are expected to slowly rise throughout surgery due to CO₂ absorption. The anesthesiologist will make specific adjustments and alter ventilation settings throughout the surgery to prevent the values from elevating further once they reach 37-38 mmHg. Between 33-36 mmHg, no adjustments are made. Therefore, we will also examine the valve and valve-less trocar groups on their ability to maintain acceptable arterial blood gas (ABG) levels by comparing the number of interventions required by the anesthesiologist during the procedure between groups.

Aim #2) Compare the maximum intraoperative pneumoperitoneal pressure (mmHg), smoke evacuation quality (categorical), and overall operative times (minutes) between the conventional and valve-less trocar groups.

Aim #3) Compare pain scores through discharge from the preoperative and post-anesthesia care units (PACU) by monitoring self-reported pain ratings using an 11-point numerical rating scale (NRS-11) and pain medication usage via morphine equivalent dose (MED) units.

Table 1. Definitions of key variables.

Variable	Definition	Unit
CO ₂ absorption rate	Not directly measurable. We are using end tidal CO ₂ and PaCO ₂ to indirectly measure the absorption rate.	N/A
Arterial Blood Gases (ABGs)	Measurement of the pH level and the bicarbonate, oxygen, and carbon dioxide concentrations in arterial blood (HCO ₃ , PaCO ₂ & PaO ₂); important in diagnosis of	N/A

	many respiratory diseases.	

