HCO ₃	Amount of bicarbonate in the arterial blood. This is used to aid in diagnosis of metabolic acidosis or alkalosis.	mmol/L
PaO ₂	Partial pressure of oxygen in the arterial blood. This is the true measure of O ₂ build in the blood.	mmHg
PaCO ₂	Partial pressure of carbon dioxide in the arterial blood. This is the true measure of CO ₂ build up in the blood, and reflects whether the lungs are keeping up in expelling the extra CO ₂ from abdominal absorption.	mmHg
End tidal CO ₂	The level of carbon dioxide in the air exhaled from the body, as measured by the ventilator. Essentially, this reflects the amount of CO ₂ that the lungs are expelling due to CO ₂ absorption from the insufflations. This increases over the course of the procedure.	mmHg
"Blunted" end tidal CO ₂	A technical observation made regarding the shape of the end tidal CO ₂ curve on the capnogram displayed on the ventilator. This is an observation, not discretely measureable.	N/A
Tidal volume	The lung volume representing the normal volume of air displaced between normal inspiration and expiration when extra effort is not applied (i.e., normal/resting breathing).	ml
O ₂ saturation	Measure of how much oxygen the blood is carrying as a percentage of the maximum it could carry.	%
Pneumoperitoneal pressure	Measurement of air or gas in the abdominal (peritoneal) cavity.	mmHg
Peak inspiratory pressure (PIP)	Point of maximal airway pressure.	mmHg
Positive end-expiratory pressure (PEEP)	Pressure maintained in airways at end of exhalation.	mmHg
Smoke evacuation quality	Smoke evacuation occurs during surgical procedures where there is tissue ablation. Smoke evacuation systems capture the plume (smoke comprised of carbonized cell fragments, water vapor, and hydrocarbons) from vaporized tissue near its origin before it becomes air-dispersed and deposits in the respiratory tracts of the surgical team.	Categorical (see Appendix B)

2.0 - METHODS

2.1 - Study Population

Adult male patients \geq 18 years of age with prostate cancer who are eligible and electing to undergo robotic prostatectomy surgery at OhioHealth Dublin Methodist Hospital between March 1, 2016 and February 28 2017 (12 months). Exclusion criteria to robotic surgery include:

- 1) Cirrhosis or liver failure (Child-Pugh class A, B, or C) or clinical suspicion of liver failure
- 2) Ascites
- 3) Uncontrolled diabetes [as reported by the pre-anesthesia testing (PAT) physician]

4) Renal insufficiency (serum creatinine level > 3.0 mg/dl)

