Exclusion criteria to participation in this study include:

- 5) Age < 18
- 6) Emergency surgery
- 7) Persons not capable of providing informed consent
- 8) Persons participating in any other research study involving an investigational drug or device or investigational surgical procedure that could interfere with the physiologic parameters being collected (for example, a study evaluating different anesthesia regimens that could confound study results).
- 9) Non English-speaking

2.2 - Hypothesis

It is hypothesized that the AirSeal® System will allow for lower CO₂ absorption rates than the Xcel® System. Furthermore, lower variance in pneumoperitoneal pressure will allow for less "over-pressure" events and peritoneal stretch, which may reduce postoperative pain. Pain will therefore also be assessed through self-report and post-operative pain medication usage (see Table 4 & Appendix A), and analyzed in comparison between both groups.

The term "over pressure" refers to times when the measured pressure in the peritoneal cavity exceeds the set pressure on the insufflator. In such cases, the standard insufflation systems will stop the flow of CO₂ into the abdomen through the port and will actively vent gas to reduce the pressure back to the set point (usually 10mmHg with a maximum of 20mmHg). This "over pressure" theoretically should not occur with the AirSeal® system because the lack of a valve on the port allows gas to escape immediately when the pressure rises (e.g. abdominal muscle contractions when anesthesia is light) so that the pressure does not exceed the set level. "Peritoneal stretch" refers to stretching of the peritoneum (lining of the abdominal wall) from insufflation of the abdomen. The higher the pressure of the pneumoperitoneum/intra-abdominal pressure, the more stretch there will be of the peritoneum with potentially more postoperative pain.

We intend to analyze the results of a total of 100 patients randomized to either the AirSeal® system or conventional trocars.

2.3 - Study Variables & Outcomes of Interest

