Recruitment will occur either at the preoperative office/clinic visit, in the office setting, or in the pre-anesthesia testing office visit (PAT). The study will be explained to the potential subject with ample opportunity to ask questions and consider participation. Recruitment will occur prior to administration of any narcotic or sedative medications. Each potential subject will provide written informed consent prior to any research-related procedure, recording/documenting, or activity occurring. An individual's consent to participate will be documented on the IRB-approved informed consent form. The original executed consent form will be retained in the Principal Investigator's study files; a copy will be given to the subject to retain. The original copy will be kept in a locked cabinet along with all study documents that contain private subject information.

Following informed consent, patients will be randomized and prepared for surgery per standard institutional policy and practice. Prior to the start of the study, the study site will set up a computer based randomization system that will randomize subjects into either one of the two groups. Based on the randomization sequence, either the AirSeal® System or a conventional insufflator and trocar will be inserted per the surgeon's normal operative procedures and care (i.e., Endopath® port with standard insufflation). A total of one AirSeal® Access Port will be used on any one subject. For every control subject, one 5mm or larger port used will be designated and recorded as the "study" port. [name] will be the only surgeon performing these procedures, eliminating variation in technique between surgeons. The AirSeal® port is 5mm in size and the standard insufflation port is 12mm in size, so the study population will not be subjected to larger port sizes than they would if off-study.

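### Lung disease is neither an exclusion, a stratification factor nor a planned covariate, which adds noise and overdispersion to the Aim 1 comparison, above all to the Poisson test of the intervention count

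*Combined protocol and SAP*

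**What the plan says.** Section 2.1 has two lists. The first, headed "Exclusion criteria to robotic surgery include", covers liver disease, ascites, uncontrolled diabetes and "Renal insufficiency (serum creatinine level > 3.0 mg/dl"). The second, headed "Exclusion criteria to participation in this study include", holds items 5 to 9. Only item 8 is aimed at confounding of the physiology: it bars other studies "that could interfere with the physiologic parameters being collected". No item in either list concerns the lungs or sets a baseline PaCO₂ or end-tidal CO₂ limit.

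Section 1.2 states: "The primary observation to be made is the level of PaCO₂ in the arterial blood". Table 1 explains that PaCO₂ "reflects whether the lungs are keeping up in expelling the extra CO"₂ absorbed from the abdomen. Ventilator adjustments begin once values reach 37-38 mmHg, and each adjustment is counted. Section 2.3 expects little difference in blood gases and says the valve-less port will be judged better if the standard arm needed more ventilator changes to hold them.

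On allocation, section 2.4 says that "the study site will set up a computer based randomization system that will randomize subjects into either one of the two groups". It states no ratio, blocking or stratification factor. The first blood gas is drawn at catheter insertion (Table 3), which follows randomization.

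In section 2.5, CO₂ and PaCO₂ are described as changes over three intervals, two of them from baseline. The count is compared by Poisson regression, or by a zero-inflated model if many patients need no intervention. A characteristic enters the analyses only if it differs significantly between groups.

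**The concern.** By the protocol's own definition, PaCO₂ measures clearance as well as absorption, so chronic lung disease is a comorbidity that acts directly on the Aim 1 measures. A man who already sits above 37-38 mmHg meets the trigger for intervention before any gas is insufflated, whichever port he receives.

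This matters most for the intervention count. It is the only Aim 1 measure with a formal test, and section 2.3 rests the device conclusion on it if blood gases turn out alike. Poisson regression assumes that, within an arm, the variance of the count equals its mean. A minority of men with much higher counts breaks that assumption and makes the standard error too small. The zero-inflated alternative deals with surplus zeros, not with a heavy upper tail.

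**Working it through.** **Inputs.** From the documents: 100 patients in total and significance at p<.05. Assumed, because the documents are silent: 50 per arm, a two-sided test, a proportion p = 5-15% of men with relevant lung disease, an intervention rate k = 2-3 times that of other men, and m = 2-3 interventions per man otherwise. For PaCO₂: SD 4 mmHg in the other men and a shift s = 5-8 mmHg in affected men. The plan gives no power, effect size, SD or event rate, so it has no figure of its own to reproduce.

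**1. Bias.** Simulation with no device effect (40,000 trials per scenario, p up to 20%) gave an average estimated rate ratio of 0.998-1.002. There is no systematic shift.

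**2. False-positive rate of the count test.** With the two kinds of men mixed, mean = m[1 + p(k−1)] and variance = mean + m²(k−1)²p(1−p). The variance-to-mean ratio is therefore

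φ = 1 + m(k−1)²p(1−p) / [1 + p(k−1)].

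An unadjusted Poisson test compares with 1.96 when it should compare with 1.96√φ. Its true error rate is P(|Z| > 1.96/√φ).

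| p | k | m | φ | 1.96/√φ | error rate |
|---|---|---|---|---|---|
| 5% | 2 | 2 | 1 + 2×0.0475/1.05 = 1.09 | 1.88 | 6.0% |
| 10% | 3 | 2 | 1 + 8×0.09/1.2 = 1.60 | 1.55 | 12.1% |
| 15% | 3 | 3 | 1 + 12×0.1275/1.3 = 2.18 | 1.33 | 18.4% |

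The range is about 6-18%. Simulation agrees over its wider range (5.9-20.2% with p up to 20%). With a robust variance the simulated rate is 5.2-5.7%. With lung disease as a covariate in the Poisson model it is about 5%.

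**3. Power for the count.** A robust variance protects the error rate but does not remove the noise. At a true rate ratio of 0.7 with m = 3, simulated power with the robust variance is 80% without affected men and 65% with p = 10%, k = 3.

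**4. Chance imbalance.** With two independent Binomial(50, p) counts, the probability that the arms differ by 4 or more affected men is 10%, 24% and 32% at p = 5%, 10% and 15%. If the total is instead fixed at 5 or 10 affected men, the figures are 6% and 32%. When a gap of 4 or more occurs, Fisher's exact test reaches p<.05 in only about 7% of cases. For example, 3 against 7 of 50 gives p = 0.32. With k = 3 that split alone produces a rate ratio of (50 + 7×2)/(50 + 3×2) = 64/56 = 1.14.

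**5. Raw PaCO₂ levels.** Variance inflation = 1 + p(1−p)s²/16. It runs from 1 + 0.0475×25/16 = 1.07 to 1 + 0.1275×64/16 = 1.51, so 100 patients carry the information of 93 down to 66. This holds for raw 60-minute levels only. The planned description is of change, and a shift already present at baseline cancels from the two intervals that start there.

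**The case against.** **Randomization.** A reader might infer that PaCO₂ and the counts would reflect lung disease rather than the device. The documents do not support that. Allocation is random, so lung disease falls equally on both arms in expectation, and step 1 shows no bias. This stands, and it limits the point to precision and validity of the test.

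**PaCO₂ is planned as a change.** Section 2.5 specifies no between-arm test of PaCO₂ level, so the 7-51% inflation overstates the harm to what is planned. If 0-2 mmHg of the shift survived in the change score (SD kept at 4), inflation would be at most 1 + 0.1275×4/16 = 1.03. Even on raw levels, four extra affected men move an arm mean by 4/50 × 5-8 = 0.40-0.64 mmHg, against a standard error of 4√(2/50) = 0.8 mmHg. This stands too. It does not reach the count, which has no baseline value to subtract.

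**Eligibility.** It is tempting to say that the study chose to screen liver, kidney and diabetes and overlooked the lungs. Those items are exclusions from robotic surgery in general. The documents do not say whether pre-anesthesia testing already turns away men with severe lung disease, so entry of CO₂ retainers is possible but not shown. Broad eligibility is also a defensible choice for a device in routine use.

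**Inputs.** Prevalence, shift and rate multiplier are all assumed, and the larger values may fit only a few of the men who have some lung disease. That is fair, and it is why a range is given.

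**Existing safeguards.** Medical history is collected, and significant imbalances will be accounted for. But no lung field is named, Table 2 files the baseline blood gas under intraoperative data, and step 4 shows that the significance screen would rarely react.

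**Conclusion.** The concern holds in a limited form. The plan has no pulmonary exclusion, no stratification by lung disease and no prespecified lung-disease or baseline-CO₂ covariate for outcomes that depend on CO₂ clearance. The consequences are extra noise, a real chance of an imbalance that the section 2.5 screen would miss, and a Poisson test of the count that is too liberal: about 6-18% false positives instead of 5%. Those figures assume 50 per arm, 5-15% of men affected, 2-3 times the interventions in them and a mean of 2-3 otherwise. If few such men enter, or if their counts are hardly raised, the effect is small. The PaCO₂ description is largely protected by its change-from-baseline form, except against a steeper rise in men with poor clearance. The change is worth making because it is cheap and protects the measure on which the device conclusion may rest.

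**What to change.** - **Section 2.3, Table 2(a) item 8:** record documented chronic lung disease (yes/no) as a named field within the medical history already collected.
- **Section 2.4:** stratify the computer randomization by that field, with blocks within each stratum, since simple randomization within strata would not balance it. The field must come from the history because the first blood gas follows allocation.
- **Section 2.5, Aim 1:** include the lung-disease factor and the baseline (pre-insufflation) PaCO₂ and end-tidal CO₂ as prespecified covariates in any between-arm comparison, whether or not the arms differ significantly. Analyse the intervention count with a robust variance or a negative binomial model.
- **Section 2.1:** state whether the absence of a pulmonary criterion is deliberate, and whether pre-anesthesia testing already screens for lung disease. Whether to exclude known CO₂ retainers is left to the investigators: it would narrow the population to which the results apply, and the other changes do not depend on it.

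The cost is a short amendment, one extra randomization field and slightly more analysis work.

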The following data points are all routinely collected for patients who choose to undergo robotic prostatectomy, via the OhioHealth electronic medical record, CareConnect. We will collect similar data points for patients electing enrollment in this trial which include the following listed below (Tables 2-4). Data points which are not collected in the standard of care setting are noted below in **bold face type**. Only the study staff will have access to the database created solely for use in this study. Data will be de-identified following study completion, prior to statistical analysis.

Table 2. Study Variables by Operative Time-point

(a) Preoperative data [collected at the preoperative office/clinic visit, in the office setting, or in

the pre-anesthesia testing (PAT) office visit]:

- 1) Medical record number
- 2) Patient name
- 3) Patient date of birth
- 4) Phone number
- 5) Email address
- 6) Body mass index (BMI)
- 7) Weight (lb)
- 8) Medical history
- 9) Surgical history (major only)
- 10) Serum creatinine (most recent prior to surgery) (mg/dl)
- 11) Hemoglobin (g/dl)
- 12) Preoperative pain measured by the NRS-11 (Appendix A)**

(b) Intraoperative data:

- 1) Details of the surgical procedure
- 2) The number, size(s), and locations of ports used (standard protocol vs. deviation from standard protocol)
- 3) Values obtained from anesthesia report at baseline, 60 minutes after insufflations, and at the end of procedure and mean and standard deviation calculated from continuously recorded values:
 - a) End tidal CO₂ (mmHg)
 - b) O₂ saturation (%)
 - c) Respiratory rate
 - d) Blood pressure
 - e) Heart rate
 - f) Tidal volume (ml)
 - g) PIP (peak inspiratory pressure) (mmHg)
 - h) PEEP (positive end-expiratory pressure) (mmHg)
- 4) CO₂ absorption rate via arterial blood gases (ABGs) at baseline, 60 minutes after insufflations, and at the end of the procedure [PaCO₂ (mmHg), HCO₃ (mmol/L) & PaO₂ (mmHg)]
- 5) Number of times the anesthesiologist intervenes to adjust ventilation settings throughout the surgery to prevent the values from elevating further once they reach 37-38 mmHg
- 6) Estimated blood loss (EBL, in ml)
- 7) Core body temperature (after trocar placement, at 30 minutes, at 60 minutes, and at end of procedure; Fahrenheit)
- 8) Insufflation time (minutes)

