For item (b)3, continuous values will be exported into individual patients-specific Excel spreadsheets with the assistance of the CareConnect Systems Analysts. This is due to the fact that there are far too many data points (ET CO₂, O₂ saturation, RR, BP, HR, TV, PIP, PEEP, every 1 minute for 120 minutes) to be manually extracted and subsequently manually entered into the Data Collection Tool by study staff. The biostatistician will perform individual analyses on these data sets, and calculate means and standard deviations to be entered into the Data Collection Tool.

For item (d)4, we are evaluating for oliguria in the immediate post-operative period (1900-0700 hours). Oliguria is infrequently viewed as a complication of laparoscopic surgery. The rate of urine output in

healthy patients undergoing laparoscopic surgery is measured during the period of CO₂ pneumoperitoneum and for several hours after desufflation. For patients that are discharged prior to the completion of the urine output collection (i.e., prior to 0700 hours postoperatively), they will be instructed to take home their urine collection canister and collection instructions to complete measurements following discharge. The Research Coordinator will then call the patient the following morning for the urine output measurement.

Table 3. Arterial Blood Gases (ABGs) monitoring schedule by anesthesiologist.

Timepoint	Definition
Baseline	At insertion of the catheter
60 minutes	60 minutes after insufflations
End of the procedure	Immediately at the end of surgery

We will be measuring the trend in arterial blood gases over time (Table 3). Optimal intraoperative levels for PaCO₂ and end tidal CO₂ should be between 33-37 mmHg. These values are expected to slowly rise throughout surgery due to CO₂ absorption. The anesthesiologist will make specific adjustments and alter ventilation settings throughout the surgery to prevent the values from elevating further once they reach 37-38 mmHg. Between 33-36 mmHg, no adjustments are made.

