Since the anesthesiologist will be adjusting ventilator settings at 37-38 mmHg to typically keep the end tidal CO₂ below 40 mmHg, we expect that there will not be a large amount of difference between standard and valve-less trocars regarding the ABGs. However, the ABGs will change over time, warranting the alteration of ventilator settings by the anesthesiologist. In other words, if the ABGs are same between the two groups but the anesthesiologist had to increase the respiratory rate or tidal volume to keep end tidal CO₂ low more so in the standard group than the valve-less, then we will conclude that the valve-less was better. Essentially, the ABGs are a sort of "control" whereby even if they are not different, it still allows us to know whether or not there was a real physiologic difference occurring, whether or not we saw a difference in the other measures that were adjusted in real time.

Table 4. Pain monitoring schedule by Pre-op and PACU RNs using NRS-11.

Timepoint	Definition
Baseline	Prior to surgery
Post-operatively	After surgery & after anesthesia completion
30 minutes post-operatively	30 minutes after surgical completion time (+/- 5 minutes)
60 minutes post-operatively	60 minutes after surgical completion time (+/- 5 minutes)
At discharge	Immediately prior to discharge from the PACU

Postoperative (post-anesthesia) pain will be evaluated at baseline, post operatively, once every thirty minutes for the first hour and every 8 hours until discharge (Table 4). Floor nurses (preoperative and PACU) will record pain scores reported by patients during structured interviews using an 11-point numerical rating scale (NRS-11), in which a rating of 0 corresponds to no pain, ratings of 1-3 indicate mild pain, 4-6 indicate moderate pain, and ratings of 7-10 correspond to severe pain (Appendix A).

Data will be collected using the forms in the Appendix. Data will be collected by a member of the research team (clinic nurse or clinical research coordinator). All data will be coded by subject number and de-identified. The designated clinical research coordinator will hold the key to subject codes in a locked cabinet and password-protected electronic file. Case reports formed with the coded key will be available only to the study staff.

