Standard operative procedures will be followed regardless of randomization sequence or participation in the study (e.g., standard of care procedures). If a technical malfunction of the AirSeal® iFS or AirSeal® Access Port were to occur, the surgeon would replace both with a conventional insufflator and trocar. Documentation of the AirSeal® malfunction will be made and the subject will be followed for safety purposes, but no further study data will be recorded. All ports will be placed according to standard care. All clinical decisions will be made per standard practice and policy. One trocar per patient will be randomized between the Endopath and AirSeal® trocars. The other trocars used for the procedure will be standard (5 standard plus 1 randomized for a total of 6) and will not vary for patients on the study as compared with typical robotic prostatectomy patients.

A standardized anesthesia regimen will be followed in order to create a uniform population. The anesthesia regimen is typical for this type of surgery. Subjects will be given midazolam (2.0 mg) for pre-induction. Fentanyl (up to 1.5 mcg/kg), propofol (up to 2.0 mg/kg) and rocuronium (as needed for neuromuscular blockade) will be used for anesthesia. Anesthesia will be maintained with sevoflurane and/or deflurane and oxygen. Fentanyl (2-3 mcg/kg/hr or 0.7 mcg/kg boluses) will also be used for anesthesia maintenance. A dose of ondansetron (4 mg) will be given for nausea and vomiting prophylaxis and a dose of ketorolac (15-30 mg) will be given for pain prophylaxis. Glycopyrrolate and neostigmine will be used for anesthesia reversal. Postoperatively, ketorolac, oral Percocet, and/or Tylenol Extra Strength (ES) will be given as needed to treat pain. Ondansetron will also be given as needed for nausea control.

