Along with standard anesthesia regimen, the anesthesiologist during the case will take arterial blood gases (ABGs). An arterial line will be placed since the subject is in the prone position to keep close surveillance on perfusion pressure. An arterial line is not placed in all robotic prostatectomy patients and is used in those who require more careful and continuous blood pressure monitoring. For the study, all patients who consent to participate will have an arterial line. An arterial line is a very small catheter similar to an IV catheter used in all surgical procedures but placed in an artery instead of a vein. It will be placed by anesthesia (not nursing). The risks are similar to an IV, such as bruising/bleeding/hematoma at the site of insertion. The arterial line will be removed at the end of the operation per routine practice unless required for postoperative blood pressure monitoring in PACU. The arterial line kit cost will be accounted for in the study budget. If in the opinion of the anesthesiologist an arterial line is not feasible, a 20 gauge needle catheter will be placed in the radial artery post-induction for samples to be taken intermittently during the surgery.

Samples will be taken at baseline beginning at insertion of the catheter, 60 minutes after insufflations, and at the end of the procedure. ABGs will be analyzed for PaCO₂, HCO₃, PaO₂ and pH. Study staff will document all values that are produced from ABGs. Data points (such as PIP, PEEP, end-tidal CO₂ etc.) from the anesthesia machine will be automatically uploaded into CareConnect. Subjects will undergo their surgical procedure regardless of participation in this study. The AirSeal® System is commercially available and in clinical use. There are no additional direct costs to participants in this study. The principal risk specifically associated with participation in this study is potential loss of confidentiality. Participants in this study are not exposed to any additional or different risks associated with the surgery. If randomized to the AirSeal® System, potential benefits to participation in the study include decreased need for port removal for removal of foreign bodies and native tissues, placement of prosthetics, and scope de-fogging and smoke evacuation.

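### The tested Aim 1 count depends on who the anesthesiologist is, but the provider is not held constant, listed in Table 2 or modelled, so plain Poisson standard errors may be too small

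*Combined protocol and SAP*

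**What the plan says.** **Surgeon.** Section 2.4 says that one named surgeon "will be the only surgeon performing these procedures, eliminating variation in technique between surgeons".

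**Aim 1 count.** Table 2(b) item 5 in section 2.3 collects the "Number of times the anesthesiologist intervenes to adjust ventilation settings throughout the surgery to prevent the values from elevating further". Section 2.5 compares this count between trocar groups by Poisson regression at p<.05, with a zero-inflated model if many patients need no intervention. The CO₂ changes are only described, so this is the one between-arm test under Aim 1.

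**Weight of the count.** The text after Table 3 in section 2.3 expects little difference in blood gases. If they are equal but more ventilator adjustment was needed in the standard arm, "then we will conclude that the valve-less was better".

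**Provider.** Section 2.4 identifies the provider by role only: "the anesthesiologist during the case will take arterial blood gases". The randomization system "will randomize subjects into either one of the two groups", and no stratification factor is stated. Table 2 lists no provider identifier. Covariate adjustment in section 2.5 is confined to demographic and pre-operative clinical characteristics that differ significantly between arms, so the provider is not a candidate.

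**What limits discretion.** Sections 1.2 and 2.3 give a shared trigger: the anesthesiologist will "alter ventilation settings throughout the surgery to prevent the values from elevating further once they reach 37-38 mmHg", and nothing is changed at 33-36 mmHg. Section 2.4 adds: "A standardized anesthesia regimen will be followed in order to create a uniform population".

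**The concern.** The plan treats operator variation as a threat and removes it for the surgeon. The Aim 1 count, however, records what the anesthesiologist does. The trigger says when to act. It does not say how large a step to take or how soon to take the next one, so two anesthesiologists facing the same CO₂ curve can produce different counts.

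If several providers share the 100 cases and differ in habit, the counts vary more than a Poisson distribution allows. The planned model takes the variance to equal the mean, so its standard error would be too small and its p-value too optimistic. That matters because this count can settle the trial's conclusion when the blood gases agree.

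**Working it through.** **Inputs from the documents.** Total 100 patients (section 2.2), two groups, Poisson regression, p<.05. No power, effect size or expected count is stated, so there is no planned figure to reproduce.

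**Assumptions.** 1:1 allocation (50 per arm), two-sided test, mean count μ = 4, K = 4 or 8 anesthesiologists, and normally distributed provider log-rates with SD s. Two providers at +1 and -1 SD differ by a factor e^(2s): 1.49 at s = 0.2, 1.82 at s = 0.3 and 2.72 at s = 0.5.

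**Step 1: chance imbalance.** With four providers of 25 cases each, a given provider's share differs between arms by at least 10 percentage points (a 15:10 split or worse) with hypergeometric probability 0.36. With two providers of 50 cases it is 0.32.

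**Step 2: the standard error that the plan would report.** For two groups, plain Poisson gives SE(log rate ratio) = √(1/T₁ + 1/T₀), where T is the total count per arm. With no treatment effect this is √(1/200 + 1/200) = 0.100. At a rate ratio of 0.75 it is √(1/150 + 1/200) = 0.108. Provider variance does not appear in the formula. In simulation the mean reported SE at rate ratio 0.75 was 0.108 at s = 0 and 0.110-0.112 at s = 0.5.

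**Step 3: the actual variance.** The variance-to-mean ratio is about φ = 1 + μ(e^(s²) - 1)(1 - 1/K). The false-positive rate is about 2[1 - Φ(1.96/√φ)].

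| s | φ, K = 4 | φ, K = 8 | False positives, formula | False positives, simulated |
|---|---|---|---|---|
| 0 | 1.00 | 1.00 | 5.0% | 4-6% |
| 0.2 | 1 + 4×0.0408×0.75 = 1.12 | 1 + 4×0.0408×0.875 = 1.14 | 6.4-6.7% | 5-8% |
| 0.3 | 1 + 4×0.0942×0.75 = 1.28 | 1 + 4×0.0942×0.875 = 1.33 | 8.4-8.9% | 8-10% |
| 0.5 | 1 + 4×0.2840×0.75 = 1.85 | 1 + 4×0.2840×0.875 = 1.99 | 15.0-16.5% | 13-16% |

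The simulations assigned 100 patients at random to providers and drew Poisson counts. The last column is the range over repeated runs. The formula runs a little high at s = 0.5 because it uses the average φ. At a mean count of 2 the simulated rates were lower: 6-7% at s = 0.3 and 9-10% at s = 0.5.

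**Step 4: remedies compared** (mean count 4).

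- Patient-level robust SEs without a provider term bring the false-positive rate back to about 5-7%. At s = 0.3 and rate ratio 0.75, power is then about 66-68%.
- With a provider factor and model-based SEs, the false-positive rate is about 5-8%. Power in the same setting is about 73-77%.
- If providers do not differ (s = 0), the provider factor costs about 1 to 4 points of power.

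**The case against.** The strongest reply is that discretion is already limited. Everyone works to the same 37-38 mmHg trigger and the same drug regimen, and randomization balances providers on average. This is largely right. It is a reason to expect a small provider SD, and at 0.2 the inflation is slight. It does not remove the issue, because step size and spacing are left open.

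A second reply is that overdispersion can be handled by robust or negative binomial variance with no provider ID. That stands for type I error. It leaves avoidable noise in the estimate, which is the power gap in step 4.

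Three stronger readings are tempting but not supported:

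- *Provider differences bias the comparison.* Randomization prevents systematic confounding. What remains is chance imbalance and extra variance.
- *They widen the planned confidence interval.* Under plain Poisson the reported interval barely moves. The fault is that it is too narrow, and a power loss appears only once the variance is estimated honestly.
- *Provider identity is unrecorded and lost to analysis.* The documents show only that Table 2 does not list it. Data come from the electronic record and the anesthesia report, which may hold it, and the data collection forms and tool in Appendices C and D are not in the available text.

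**Conclusion.** The point holds in a conditional form. The plan controls operator variation for the surgeon but makes no provision for the anesthesiologist, whose actions are the tested Aim 1 outcome. If providers differ, plain Poisson regression overstates the evidence in either direction. The false-positive rate stays near nominal at provider SD 0.2, is 8-10% at 0.3 and is 13-16% at 0.5.

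These figures rest on an assumed mean count of 4, four to eight providers and 50 per arm. The documents give neither the number of providers, nor the mean count, nor the size of practice differences. If one anesthesiologist covers all cases, the concern disappears. It is worth acting on because the count can decide the conclusion and the remedy is cheap.

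**What to change.** 1. Add to Table 2(b) a coded anesthesiologist ID and a record of any hand-over during the case, taken from the existing anesthesia record. Assign the code before the data are de-identified for analysis.
2. Pre-specify in section 2.5 that the Aim 1 count model includes anesthesiologist as a fixed or random effect, with patient-level robust or negative binomial variance. Carry the same term into the zero-inflated model if that is used. State in advance how providers with few cases are pooled and to whom a handed-over case is attributed.
3. Tabulate counts by arm within anesthesiologist.
4. If one anesthesiologist will cover every case, say so in section 2.4. The provider term then drops out.

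The cost is one data field, one model term and a few degrees of freedom: at most about 3-4 points of power if providers do not differ. A provider term does not define what counts as one adjustment. That is a separate matter and needs its own rule.
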